#### **8.3.4. Patients Lost to Follow-Up**

A patient will be considered lost to follow-up if he or she repeatedly fails to return for scheduled visits and is unable to be contacted by the study site. Site personnel are expected to make diligent attempts to contact patients who fail to return for a scheduled visit or were otherwise unable to be followed up by the site.

#### **8.3.5. Discontinuation of Study Sites**

Study site participation may be discontinued if Lilly or its designee, the investigator, or the ethical review board (ERB) of the study site judges it necessary for medical, safety, regulatory, or other reasons consistent with applicable laws, regulations, and GCP.

#### **8.3.6. Discontinuation of the Study**

The study will be discontinued if Lilly or its designee judges it necessary for medical, safety, regulatory, or other reasons consistent with applicable laws, regulations, and GCP.

## 9. Treatment

### 9.1. Treatments Administered

All treatments will be administered within the product labeling in China, when applicable. For LY2963016, administration is described in the protocol. This study involves a comparison of LY2963016 to Lantus® administered QD subcutaneously. Patients will continue their prestudy OAMs throughout the study.

Lantus® or LY2963016 will be started from 10 U based on randomization. Investigators will titrate insulins until a FBG  $\leq$ 100 mg/dL (5.6 mmol/L). The dosing algorithm is referred to Section 9.5. The investigators will be responsible for dose adjustment in telephone or office visits. The insulin doses can be adjusted between the intervals of visits at discretion of the investigators.

The investigator or his/her designee is responsible for the following:

- explaining the correct use of the investigational agent(s) to the patient,
- verifying that instructions are followed properly,
- maintaining accurate records of investigational product dispensing and collection, and
- returning all unused medication to Lilly or its designee at the end of the study.

Patients taking insulin secretagogues must continue taking their prescribed dose throughout the study. If the patient experiences hypoglycemia, the investigator should assess whether it can be attributed to causes other than the insulin secretagogue, such as missed meals, other changes in diet or exercise, or incorrect dosing/administration of insulin. The investigator may decrease the dose or discontinue the insulin secretagogue only after consultation and approval by the Lilly CRP or designee, and this must be documented appropriately.

Patients will be instructed to contact the investigator as soon as possible if he or she has a complaint or problem with the investigational product so that the situation can be assessed.

### 9.2. Materials and Supplies

Clinical trial materials will be labeled and should be handled and stored according to the respective country's regulatory requirements.

The reference therapy (Lantus®) used in this clinical trial is approved for use in each respective country.

Patients must continue to use their prestudy OAMs throughout the study (Section 9.8.1).

Patients on metformin must continue or discontinue the use of metformin based on Inclusion Criterion [4].

Patients randomized to LY2963016 will be provided with LY2963016 as a 100 U/mL solution for injection in a prefilled pen injector. Patients randomized to Lantus® will be provided with Lantus® as a 100 U/mL solution for injection in prefilled pen injector. In addition, a commercially available glucometer will be provided with the necessary supplies.

### 9.3. Method of Assignment to Treatment

At Visit 1, patients will be assigned a patient number, and at Visit 2, those who are eligible to participate in the study will be assigned to 1 of the 2 treatment arms in a ratio of 2:1 (LY2963016 versus Lantus®) by stratified randomization via random assignment using the interactive web response system (IWRS). To achieve group comparability, patients will be stratified by HbA1c stratum (<8.5%, ≥8.5%), and entry use of insulin secretagogues (SU, meglitinide, neither).

### 9.4. Rationale for Selection of Doses in the Study

Patients in both treatment groups will start with a single injection of basal insulin analog (either Lantus® or LY2963016). As supported by nonclinical data demonstrating similar glucodynamics between Lantus® and LY2963016 (data on file), and clinical data demonstrating similar efficacy and safety between Lantus® and LY2963016 (Blevins et al. 2015; Rosenstock et al. 2015), these insulins will be dosed in a similar fashion based on the dosing algorithm described in the protocol.

Patients will be started on 10 U of Lantus® or LY2963016, based on randomization. Investigators will titrate insulins until a FBG ≤100 mg/dL (5.6 mmol/L) is achieved as described in Section 9.5. It is expected that most of the titration will be completed during the Titration Period (Weeks 0 through 12) such that a patient is on a relatively stable basal insulin dose during the Maintenance Period (Weeks 13 through 24) during which adjustments to insulin dose would be for safety such as hypoglycemia or unacceptable hyperglycemia.

Patients will continue to use their prestudy OAMs throughout the study.

### 9.5. Selection and Timing of Doses

All treatments will be administered according to the country-specific product labeling where applicable. The starting dose for patients is 10 U QD. The study insulin will be self-administered by the patient at bedtime (approximately the same time) from the following day after Visit 2. The dosing time is chosen based on the China guideline for type 2 diabetes on initiation of basal insulin (Chinese Diabetes Society 2014).

Dose titration is investigator-driven. From the telephone visit (Visit 3), the investigator will assess the patient's glycemic control for the previous week (weekly-base titration till Visit 10 and bi-weekly titration as needed afterwards) and, if necessary, inform the patient about any needed dose adjustment. The dose will be adjusted using the following dosing algorithm based on the patient's BG.

Following initiation of LY2963016 or insulin glargine, investigators may make alterations to increase the doses recommended by the dose adjustment algorithm in situations where adjustment have not had the desired therapeutic effect after consultation with Lilly. Dose increases must be made at weekly intervals within 8 weeks from study initiation and as needed in the rest of treatment. The insulin doses can be adjusted between the intervals at discretion of the investigators.

The treat-to-target FBG is  $\leq 100$  mg/dL (5.6 mmol/L). The insulin dose titration will be based on the glucose pattern from 3 separate BG readings before breakfast (preferably most recent readings) prior to each contact/visit from previous 1-2 weeks. The dose algorithm for LY2963016 or insulin glargine will be referred to [Table ABET.9.1](#) (Davies et al. 2005).

**Table ABET.9.1. Algorithm for Titration of Basal Insulin Dose**

Average BG Before Breakfast (for Titration of Evening Dose)	Increase in Basal Dose (Units)
<70 mg/dL (<3.9 mmol/L)	Decrease to previous lower dose*
70-<100 mg/dL (3.9-5.6 mmol/L)	No adjustment
100-<120 mg/dL (5.6-6.7 mmol/L)	0-+2 U (at discretion of the investigator)
120-<140 mg/dL (6.7-7.8 mmol/L)	+ 2 U
140-<180 mg/dL (7.8-10.0 mmol/L)	+ 4 U
$\geq 180$ mg/dL ( $>10.0$ mmol/L)	+6-8 U (at discretion of the investigator)

\* The patient will be administered with the previous lower dose if he/she has documented hypoglycemia or probable symptomatic hypoglycemia.

Abbreviations: BG = blood glucose; U = unit(s).

The investigators will also have the discretion to decrease the dose if it is noted that patients are experiencing hypoglycemia. Patients will continue to take prestudy OAMs at the same dose during the study, unless described otherwise for certain conditions prespecified in the protocol (Section 9.8). The investigator may decrease the dose or discontinue the insulin secretagogue only after consultation and approval by the Lilly CRP or designee, and this must be documented on a note-to-file.

### 9.5.1. Special Treatment Considerations

There is no plan for rescue therapy in this study. Patients who do not respond to basal insulin treatment for glycemic control will be discontinued from the study as described in Section 8.3.1.

## 9.6. Continued Access to Investigational Product

The Sponsor will not provide patients with ongoing supplies of study medication after they have completed the study treatment period because LY2963016 is experimental.

## 9.7. Blinding

This is an open-label study where investigators, patients, study-site personnel, and study monitors are aware of the treatment assignment. To minimize bias, an integrated summary of data will not be provided by the actual treatment group to the study team prior to the final database lock. Unblinding of the patient study drug treatment assignment to the study team may occur in cases when an individual patient's treatment assignment may need to be revealed for evaluation of the safety information or during review of SAEs or individual patient data.

## 9.8. Concomitant Therapy

### 9.8.1. *Antihyperglycemic Medications*

Generally, patients should continue use of their OAM regimen at screening and as described in Inclusion Criterion [4] (Section 8.1). The investigator will carefully consider the potential drug-drug interactions and contraindications of the OAMs with respect to the study insulins. Patients will not be allowed any other medications to reduce BG besides those outlined in Exclusion Criterion [11] (Section 8.2).

Patients taking insulin secretagogues must continue taking their prescribed dose throughout the study. If the patient experiences hypoglycemia, the investigator should assess whether it can be attributed to causes other than the insulin secretagogues, such as missed meals, other changes in diet or exercise, or incorrect dosing/administration of insulin. The investigator may decrease the dose or discontinue the insulin secretagogues only after consultation and approval by the Lilly CRP or designee, and this must be documented appropriately.

The intent of this study is that patients not deviate from their OAM regimen and that they only use the study insulin(s) prescribed for them during the study. However, in emergencies, it may be necessary for patients to change their dose of OAMs and/or be treated with a nonstudy insulin. This will be allowed for up to 14 consecutive days. If such a situation occurs more than once during the study, or lasts longer than 14 consecutive days, a decision to keep the patient in the study should be made only after consultation between the investigator and the Lilly CRP or medical designee. The decision should be documented by a note to the investigator's file.

Please refer to Section 8.3.1 to review the criteria for discontinuation of patients.

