### **8.3.3. Patient Discontinuation from the Study**

Patients will be discontinued from the study in the following circumstances:

- If any of Exclusion criteria ([14 to 15], [17 to 20], [23], [25], and [27 to 28]) are observed or develop after entry. In this case, the patient may be discontinued from the study at the next visit, or sooner, if patient safety is the rationale for the exclusion criterion
- If there is a lack of efficacy or the need to intensify the patient's treatment (Section 9.5.1) beyond basal insulin dosing, based on investigator discretion that the patient has not had adequate progress in the reduction of HbA1c levels in spite of adequate basal insulin titration and dosing. For example: Based on investigator clinical judgment, a patient may be deemed appropriate to discontinue from the study if he/she is consistently achieving target FBG levels  $\leq 100$  mg/dL (5.6 mmol/L), but HbA1c levels remain above 8.0% on at least 2 consecutive occasions in the absence of any signs of continued improvement. Or, a patient may be deemed appropriate to discontinue from the study if he/she is not achieving target FBG levels  $\leq 100$  mg/dL (5.6 mmol/L) but is experiencing hypoglycemia that would preclude further basal insulin titration
- If the patient is off study medication for more than 14 consecutive days
- If the patient has used short/rapid-acting insulin for glucose control and management of diabetes during an acute illness/injury for more than 14 consecutive days
- If the patient enrolls in any other clinical trial involving an investigational product or enrollment in any other type of medical research judged not to be scientifically or medically compatible with this study
- Investigator Decision
  - if the investigator decides that the patient should be discontinued from the study
  - if the patient, for any reason, requires treatment with another therapeutic agent that has been demonstrated to be effective for treatment of the study indication, discontinuation from the study occurs prior to introduction of the new agent
- Subject Decision
  - if the patient or the patient's designee, for example, parents or legal guardian requests to be withdrawn from the study
- Sponsor Decision

- if Lilly or its designee stops the study or stops the patient's participation in the study for medical, safety, regulatory, or other reasons consistent with applicable laws, regulations, and GCP
- Adverse Event

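### For more than 14 consecutive days of short- or rapid-acting insulin in an acute illness, Protocol 8.3.3 requires discontinuation while 9.8.1 permits the patient to be kept

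*Protocol*

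**What the plan says.** Protocol 8.3.3 opens its list with "Patients will be discontinued from the study in the following circumstances". One entry reads: "If the patient has used short/rapid-acting insulin for glucose control and management of diabetes during an acute illness/injury for more than 14 consecutive days". That entry contains no discretion and no consultation step. The lack-of-efficacy entry in the same list, by contrast, is expressly left to the investigator's judgment.

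Protocol 9.8.1 states the intention that patients stay on their oral regimen and the study insulin, then adds that in emergencies "it may be necessary for patients to change their dose of OAMs and/or be treated with a nonstudy insulin". It continues: "This will be allowed for up to 14 consecutive days". If the situation recurs, or goes past 14 consecutive days, "a decision to keep the patient in the study should be made only after consultation" between the investigator and the sponsor physician or designee, with a note to file. The section ends: "Please refer to Section 8.3.1 to review the criteria for discontinuation of patients". Section 8.3.1 covers inadvertently enrolled patients; the discontinuation list is in 8.3.3. Sections 9.5.1 and 9.8.2 carry the same pointer to 8.3.1.

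Protocol 9.7 says that investigators know the treatment assignment. SAP Section 6 keeps summary data blinded for the sponsor's team but allows an individual assignment to become known during consultation with the investigator.

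**The concern.** Both sections use the same 14-day threshold and attach different consequences to crossing it. Two sites that each follow the protocol could treat identical patients differently, one discontinuing and the other retaining after consultation.

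The choice changes the data. A discontinued patient fails per-protocol criterion b in SAP 5.2.1. Ordinarily that patient has no Week 24 HbA1c, so the primary MMRM relies on the missing-at-random assumption and the supportive ANCOVA carries the last value forward. A retained patient supplies a Week 24 value that nonstudy insulin may have influenced. No objective criteria for retention are given, and the investigator making the case for or against it knows the arm.

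**Working it through.** The point is textual, so the main check is to set the two rules side by side.

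| Case | Protocol 8.3.3 | Protocol 9.8.1 | Same result? |
|---|---|---|---|
| Short- or rapid-acting insulin, acute illness, 14 days or less, first time | Acute-illness entry not triggered | Allowed | Yes |
| Same, more than 14 consecutive days | Discontinuation required | Retention possible after consultation | **No** |
| Second episode, each 14 days or less | No matching entry on repeat use | Consultation before retention | No direct clash |
| Emergency change of oral agent dose beyond 14 days | No matching 14-day entry | Consultation before retention | No direct clash |

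The direct conflict is the second row. It requires that the acute illness or injury also count as an emergency under 9.8.1, which many would.

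**Is there a tie-breaker?** Neither section claims precedence. The closing pointer in 9.8.1 leads to 8.3.1, so a reader who follows it does not reach the conflicting rule. Section 9.8.2 says that patients who receive excluded therapy are discontinued, but it uses the same pointer. The amendment (a) summary changes none of these sections.

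**What follows in the analysis?**
- Discontinued: out of the per-protocol set under criterion b. An early-discontinuation HbA1c is scheduled in Attachment 1 and may feed the carried-forward value. By then the patient has already had more than 14 days of nonstudy insulin.
- Retained: Week 24 HbA1c enters the primary MMRM. None of the printed per-protocol criteria a to e in SAP 5.2.1 names nonstudy insulin. SAP 5.2.7 has no rule for HbA1c after its use.

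**Size.** The plan has no figure for this point. For scale only, its design assumptions (SAP 5.1: SD 1.3, 450 completers at 2:1, so 300 and 150, margin 0.40) give:
- standard error = 1.3 × √(1/300 + 1/150) = 1.3 × 0.10 = 0.13;
- power = Φ(0.40/0.13 − 1.96) = Φ(1.12) ≈ 0.868, which agrees with the stated figure of over 85%.

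The documents give neither the frequency of prolonged nonstudy insulin nor its effect on HbA1c. As an assumption only, let f be the net between-arm excess of retained users and d the HbA1c shift in each. The treatment difference then moves by f × d.
- f = 1%, d = 0.3: 0.01 × 0.3 = 0.003, or 0.003/0.40 = 0.75% of the margin.
- f = 5%, d = 1.0: 0.05 × 1.0 = 0.05, or 0.05/0.40 = 12.5% of the margin, and 0.05/0.13 ≈ 0.4 of a standard error.

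The upper end needs frequent, clearly unbalanced use and a full one-point shift persisting at Week 24.

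**The case against.** The strongest reply is that 9.8.1 restricts retention rather than ordering it. It requires a second, sponsor-side opinion and a note to file, and it covers more ground than the 8.3.3 entry: oral dose changes, any nonstudy insulin, repeat episodes. On that view the specific 8.3.3 entry governs its own case and consultation governs the rest. The reading is reasonable, and it is right that the sections do not command opposite outcomes. But the text does not say so, and the wrong cross-reference hides the entry that would have to prevail.

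Three stronger readings are tempting and are not supported.
- A reader might see a second conflict, because 8.3.3 also says that "discontinuation from the study occurs prior to introduction of the new agent" when another effective agent is required, whereas 9.8.1 allows nonstudy insulin for up to 14 days. But 8.3.3's own acute-illness entry is triggered only beyond 14 days, so the section itself tolerates shorter use. The clause sits under investigator decision and refers to treatment of the study indication; it may be meant for lasting therapy.
- A reader might infer that poorly controlled patients could be kept on extra insulin. The conflicting rules concern emergencies and acute illness. Inadequate response has its own route in 8.3.3, and 9.5.1 states that there is no rescue therapy and that non-responders are discontinued.
- A reader might conclude that the per-protocol set has no rule for nonstudy insulin. SAP 5.2.1 refers to a trial issue management plan that was not available, so only the printed criteria can be described.

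It also stands that reconciling the sections would not remove open-label discretion in general; 8.3.3 and 9.9 leave other discontinuation decisions to the investigator.

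**Conclusion.** The concern holds in a narrow form. For more than 14 consecutive days of short- or rapid-acting insulin in an acute illness or injury, 8.3.3 requires discontinuation and 9.8.1 permits retention, with no stated precedence and a misdirected cross-reference. This is a contradiction between two operative rules, not a gap in detail. It matters because the outcome determines per-protocol membership and whether Week 24 HbA1c is observed, in a study where the investigator knows the arm.

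The effect on the noninferiority comparison cannot be quantified from the documents and is probably small. The illustrative range of 0.003 to 0.05 HbA1c points rests wholly on assumed frequencies and effects and does not carry the conclusion. Nothing here shows that the noninferiority test is invalid or that the sample size is wrong.

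**What to change.** 1. Reconcile Protocol 8.3.3 and 9.8.1 so that a given use of nonstudy insulin, defined by type, setting and duration, leads to one stated outcome. Which outcome is a clinical decision for the sponsor.
2. Correct the references to 8.3.1 in Protocol 9.5.1, 9.8.1 and 9.8.2 so that they lead to the discontinuation criteria.
3. Before database lock, identify nonstudy insulin use beyond the stated limit from the concomitant medication records. State in SAP 5.2.1 how these patients are handled in the per-protocol set, or cite the entry in the trial issue management plan if it already covers them. In SAP 5.2.7, state how HbA1c after such use enters the primary analysis.

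The cost is a protocol clarification and a few lines in the SAP. Attachment 1 already schedules concomitant medication recording at every visit, so no new visits or assessments are needed. This assumes that the records hold start and stop dates, which the documents do not state.

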### 9.8.2. *Other Concomitant Therapy*

All concomitant therapies that are part of routine care are allowed and can be used during the study.

As described in Exclusion Criteria [9 to 11] (Section 8.2), patients should not take any other BG-lowering medications of any kind that are not allowed in the study. Patients will be allowed to use any other concomitant medications they require during the study except systemic glucocorticoid therapy longer than 14 consecutive days' duration (with the exception of topical, intra-articular, intraocular, and inhaled preparations). Patients who receive excluded concomitant therapy will be discontinued from the study (Section 8.3.1).

## 9.9. Treatment Compliance

The investigator will assess patient compliance at each visit, based on a review of the patient's glycemic control, adherence to the visit schedule, dosing-titration algorithm, administration of study drug (including dosing time), completion of study diaries, and any other parameters the investigator deems necessary.

Patients who are deemed noncompliant will receive additional diabetes education and training, as required, and the importance of compliance with the protocol will be reinforced. Patients who,

in the opinion of the investigator, are deemed consistently noncompliant may be discontinued from the study. No specific study data will be collected for analysis of treatment compliance and, therefore, will not be assessed or reported.

### 9.10. Hypoglycemic Episodes

Patients should check their BG level, whenever possible, if they have symptoms suggestive of hypoglycemia. For each hypoglycemic episode, patients should record their BG level, associated symptoms, treatment, and outcome in the study diaries provided by the Sponsor via the investigator.

When instructing patients on recognition and management of hypoglycemic episodes, a **hypoglycemic episode** is defined as any time a patient feels that he/she is experiencing a sign or symptom that is associated with hypoglycemia, or has a BG level of  $\leq 70$  mg/dL ( $\leq 3.9$  mmol/L), even if it was not associated with signs, symptoms, or treatment consistent with current guidelines (ADA 2005).

Note: Episodes of severe hypoglycemia reported during the study should also be recorded as SAEs (Section 10.3.1.1).

**Severe hypoglycemia:** An event requiring assistance of another person to actively administer carbohydrate, glucagon, or other resuscitative actions. During these episodes, the subject has an altered mental status, and cannot assist in his/her care, are semiconscious or unconscious, or experience coma with or without seizures, and may require parenteral therapy. Blood glucose measurements may not be available during such an event, but neurological recovery attributable to the restoration of BG concentration to normal is considered sufficient evidence that the event was induced by a low BG concentration (BG  $\leq 70$  mg/dL [ $3.9$  mmol/L]).

**Nocturnal hypoglycemia:** Any hypoglycemic event that occurs between bedtime and waking.

